4.1.1. Study Visits

Pilot Study

Visit 1

During screening visit, taste test and questionnaires regarding taste and dietary habits will be conducted. The sensory test includes: testing of general taste perception for the five basic tastes—salty (sodium chloride), bitter (caffeine), sour (citric acid), sweet (sucrose), and umami (glutamate)—as well as the metallic taste (ferrous sulfate), testing the detection and recognition thresholds for the different taste sensations, and testing the intensity of the bitter taste of various caffeine solutions with and without the addition of homoeriodictyol. The survey of patients regarding their taste perception and preference for foods with specific taste sensations will be conducted using a questionnaire. This questionnaire is based on the questions by McGettigan et al. [10] and has been supplemented with questions regarding the preference for and consumption of specific foods (attached in the appendix). The dietary intake surveys will be conducted using 24-hour recalls. Following an initial in-person interview, the remaining dietary intake surveys will be conducted by telephone once a week. In addition, the patients will receive a diary in which they will document their daily food intake and symptoms.

Visit 2

Before the first cycle of chemotherapy, taste test and questionnaires regarding taste and dietary habits are conducted. The sensory test includes: testing of general taste perception for the five basic tastes—salty (sodium chloride), bitter (caffeine), sour (citric acid), sweet (sucrose), and umami (glutamate)—as well as the metallic taste (ferrous sulfate), testing the detection and recognition thresholds for the different tastes, and testing the intensity of the bitter taste of various caffeine solutions with and without the addition of homoeriodictyol. The interviews with patients regarding their taste perception and preferences for foods with specific tastes will be conducted using a questionnaire. This questionnaire is based on the questions by McGettigan et al. [10] and has been supplemented with questions regarding the preference for and consumption of specific foods (attached in the appendix). The dietary intake surveys will be conducted using 24-hour recalls including assessment of physical activities within the last seven days. Following an initial in-person interview, the remaining dietary intake surveys will be conducted by telephone once a week. Blood samples for zinc measurement and determination of the chemotherapeutic agent will be collected as part of a routine blood draw.

Visit 3

During the visit for the third cycle of chemotherapy, the following tests will be repeated: testing of general taste perception for the five basic tastes—salty (sodium chloride), bitter (caffeine), sour (citric acid), sweet (sucrose), and umami (glutamate)—as well as the metallic taste (ferrous sulfate), testing of the detection and identification thresholds for the different taste sensations, and testing of the intensity of the bitter taste of various caffeine solutions with and without the addition of homoeriodictyol. Patients will be interviewed about their taste perception and preferences for foods with specific taste sensations using a questionnaire (see Appendix). Blood samples for zinc determination and quantification of the chemotherapeutic agent will be collected as part of routine blood draws prior to the start of chemotherapy administration. As part of this monitoring, serial saliva samples will be collected to analyze the concentration of the chemotherapeutic agent before, during, and after chemotherapy administration. Saliva samples will be collected before the start of chemotherapy administration ($t=0$), during chemotherapy administration ($t=2h$), at the end of chemotherapy administration ($t=4h$), two hours after the end of chemotherapy administration ($t=6h$), and the following morning ($t=18-20h$). The diary is returned by the patients.

RCT

Visit 1

The patient returns for screening one week after her last cycle of chemotherapy due to suspected bitter phantogeusia. The patient's bitter phantogeusia is determined by directly asking about bitter taste perception ("Did you notice an increased bitter taste during the course of chemotherapy?") and subsequently classifying the increased perception as "mild," "moderate," or "severe." If the patient rates her heightened perception of bitterness as "moderate" or "severe," meets all inclusion and exclusion criteria, and consents to the study by signing the patient information form, she is eligible for inclusion in the study. As part of the screening examination, the threshold for bitter perception and the bitter perception triggered by 500 ppm caffeine are recorded. Body composition is also measured using the BOD POD® and a weight check is performed. Quality of life is assessed using the EORTC-QLQ-30 Ovar and OV-28, and dietary intake is assessed using a 24-hour recall questionnaire (GloboDiet). In addition, perception of the other four basic tastes (sweet, sour, salty, umami) is determined using a sensory test. Furthermore, the patient is given a detailed explanation of the necessary follow-up visits required as part of the study and is handed a diary.

Visit 2

The patient returns for a follow-up visit three weeks after the end of her last course of chemotherapy. A test is conducted to assess bitterness perception of 500 ppm caffeine and to determine the bitterness perception threshold, as well as a sensory test to assess perception of the taste qualities sweet, sour, salty, and umami, a quality-of-life assessment using the EORTC-QLQ-30 Ovar and OV-28, and a dietary intake assessment using the 24-hour recall questionnaire (GloboDiet).

Visit 3

The patient returns 12 weeks after the end of her last chemotherapy session for a final examination. A test of bitterness perception using 500 ppm caffeine and determination of the bitterness perception threshold is performed, along with a sensory test to assess perception of the taste qualities sweet, sour, salty, and umami, a measurement of body composition using the BOD POD®, and a weight check. Quality of life is assessed using the EORTC-QLQ-30 Ovar and OV-28, and dietary intake is assessed using a 24-hour recall questionnaire (GloboDiet). The diary is discussed and collected.

RCT: Overview of Study Visits

	CRF	QoL (EORTC 30 and OV-28)	Medication dispense/return	Sensory test	BOP POD	Weight	Diary	24-hour recall
V1 (1 week after CHT)	X	X	X	X	X	X	X	X
V 2 (2 weeks after V1)	X	X	X	X			X	X
V3 (12 weeks after V1)	X	X	X	X	X	X	X	X

4.1.2. Withdrawal from the study

Patients may withdraw from the study at any time without providing a reason. Withdrawal is defined as premature termination of the study prior to attending Visit 3. Every withdrawal is documented. Documentation up to the point of withdrawal must be complete. Patients who withdraw from the study will not be replaced. Patients who withdraw from the study will be included in the statistical analysis (intention-to-treat analysis). Patients who withdraw from the study must return all remaining study medication and will continue regular follow-up after gynaecologic cancer treatment at the Medical University of Vienna.

4.1.3. Study Exclusion

Study exclusion refers to the exclusion of the patient from the study by the investigator (Associate [name] [name]). This occurs in the following cases:

- Occurrence of severe adverse events that seriously endanger the patient's health or life
- Other medical indications
- Demonstrable non-compliance by the patient
- Violation of the study protocol that, in the opinion of the investigator or the sponsor, is incompatible with the continuation of the study.

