The 20 ml mouthwash solution (depending on randomisation, either water containing 30 mg HED, food colouring, a opacifier and a carrier, or just water containing food colouring, a

opacifier and a carrier as a placebo) is administered three times daily before each main meal throughout the entire 12-week study period. The patient may discontinue treatment at any time if side effects occur, but must report this immediately to the study team. Should the patient discontinue the mouthwash, the study medications must be returned.

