4.4. Experimental design and schedule

4.4.1. Investigation of the perception of bitter taste

In ovarian cancer patients with chemotherapy-induced bitter phantogeusia, the perception of bitterness from caffeine is tested. To this purpose, study participants are administered 20 ml of an aqueous mouthwash solution containing 500 ppm caffeine. After rinsing and spitting out the caffeine solution, the patients rate the bitterness of the solution on a scale from 0 (slightly bitter) to 10 (very bitter). The perception of bitterness is then tested in the presence of HED by administering a 500 ppm caffeine rinse solution with 100 ppm HED added. After rinsing and spitting out this caffeine-HED solution, the patients again rate the bitterness on a scale of 0 to 10. The perception of bitterness of caffeine alone and of caffeine after HED is used for comparison between groups and visits. In addition, a threshold test for bitter taste is carried out to determine the concentration of caffeine at which the patients perceive a bitter taste. To determine this, the patients taste mouthwash solutions one after the other, starting with water, at increasing concentrations of caffeine. Patients indicate the concentration at which they first detect a taste (detection threshold) and the concentration at which they can recognize a specific taste (recognition threshold), and whether the taste intensifies from one concentration to the next. The resulting threshold value for bitter perception is also used for comparison between groups and visits.

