The efficacy of the treatment is defined as a reduction in the perception of bitterness by more than 30% in the treatment group compared to the placebo group. The primary endpoint will be evaluated using a paired t-test.

This will be evaluated in two analyses:

- Intention-to-treat analysis: Inclusion of all patients who used the mouthwash at least once
- Per-protocol analysis: Inclusion of patients who completed the study according to the study protocol

Secondary endpoints are also analysed using intention-to-treat and per-protocol analyses. The collected clinical and pathological data are presented descriptively using absolute values or, depending on the normality of the distribution, using the median (interquartile range) or mean (standard deviation). Metric variables are compared using Student's t-test or the Mann-Whitney U test, depending on normal distribution. Categorical variables are compared using the chi-square test and, if feasible given the number of groups, presented including the odds ratio (95% confidence interval). The study will investigate predictive factors for response to the intervention. These analyses are performed using a multivariate binary logistic regression model. The following variables are included: patient age, number of chemotherapy cycles, patient BMI, bowel resection during the primary surgery, peripheral polyneuropathy during chemotherapy, nausea at the time of study enrolment, and diarrhoea at the time of study enrolment. Version 21.0 of the statistical software SPSS (SPSS, Inc.) is used for the statistical analysis.

Patient data is pseudonymized, documented, and analysed in accordance with current data protection regulations and is not disclosed to third parties. The data is published in anonymized and aggregated form.

C) Ethical and Legal Section

1. Ethical Aspects

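### Investigator exclusion under section 4.1.3 ends study participation, not only mouthwash use, so excluded patients stay in the intention-to-treat set without later outcome values, mainly at week 12

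*Combined protocol and SAP*

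**What the plan says.** Section 4.1.3 of the protocol states: "Study exclusion refers to the exclusion of the patient from the study by the investigator". It lists four cases:

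- "Occurrence of severe adverse events that seriously endanger the patient's health or life"
- other medical grounds
- "Demonstrable non-compliance by the patient"
- and, as a matter of judgement: "Violation of the study protocol that, in the opinion of the investigator or the sponsor, is incompatible with the continuation of the study"

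Ineligible patients are handled separately as screening failures in section 4.3.3, so I read these as reasons that arise after randomisation.

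Other sections bear on the same patient:

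- **4.1.2 (withdrawal):** "Withdrawal is defined as premature termination of the study prior to attending Visit 3". Those who withdraw are not replaced, are documented fully up to exit, enter the intention-to-treat analysis and return to routine cancer follow-up. The section does not say whether exclusion by the investigator counts as withdrawal.
- **4.1.4 (end of participation):** completion requires both attendance at all visits and use of the product.
- **4.1.6 (adverse events):** events go into the patient's diary. No rule follows them to resolution.
- **4.3.4 (dosage):** stopping the mouthwash is an act of its own: "The patient may discontinue treatment at any time if side effects occur, but must report this immediately to the study team". The product is then returned. Later visits are neither planned nor cancelled.
- **Statistical Section, 3:** "Intention-to-treat analysis: Inclusion of all patients who used the mouthwash at least once". A per-protocol set is defined alongside. No method for missing values is named.

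**The concern.** The plan commits itself to an intention-to-treat analysis, but section 4.1.3 stops collection of the data that this analysis needs. Belonging to the analysis set does not give a patient a week-12 value.

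The reasons for exclusion are not neutral. A severe reaction, or failure to use the product, arises after randomisation and can depend on what was in the sachet. If later values are missing for such reasons, the patients still measured at week 12 need no longer be comparable between arms. Excluding non-compliers from the study also does, irreversibly, what the per-protocol set already does at the analysis stage.

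There is a smaller safety side: once a patient is excluded, no stated rule requires the event to be followed to its end.

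**Working it through.** The plan gives no figure for exclusions, so there is none to reproduce. The sample size calculation plays no part here. The check is a comparison of sections, a count of endpoints and a look at timing.

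**1. Does any section supply later values?**

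| Section | What it gives an excluded patient | V2/V3 measurement after exclusion? |
|---|---|---|
| 4.1.2, if it covers exclusion | Complete records to exit, intention-to-treat membership, routine follow-up | No |
| 4.1.2, if it does not | Nothing | No |
| 4.1.4 | Routine follow-up | No |
| 4.1.6 | Diary record of events | No |
| 4.3.4 | Reporting and return of product | No |
| Statistical Section, 3 | Membership of the set after one use | No |

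The gap is there on either reading of 4.1.2.

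**2. Which endpoints are exposed?** Counted from section 3.3, with the V2 column from section 4.1.1:

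| Week-12 secondary endpoint | Comparison | Also measured at V2? |
|---|---|---|
| Bitterness of 500 ppm caffeine | Between arms | Yes |
| Overall taste perception | Between arms | Yes |
| Food intake | Between arms | Yes |
| Body composition | Between arms | No |
| Weight | Between arms | No |
| Quality of life | Between arms | Yes |
| Food intake | Within arm | Yes |
| Quality of life | Within arm | Yes |
| Diary outcomes | Within arm | Kept continuously, so partial data |

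That is 6 + 3 = 9 of 12. The other 3 (bitter threshold twice, overall taste at week 3) and the primary endpoint need only V1 and/or V2. After an exclusion between V2 and V3, only body composition and weight have no planned post-baseline value at all.

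**3. When must exclusion fall?**

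- V2 is 2 × 7 = 14 days after V1, in both the visit text and the overview table of section 4.1.1.
- V3 is 12 × 7 = 84 days after V1 in the table. In the visit text it is 12 weeks after chemotherapy with V1 at week 1, so (12 − 1) × 7 = 77 days. Section 4.1.4 allows ±3 days.
- The primary endpoint is lost only in the first 14 of 77 to 84 days. This is a calendar window, not a probability.
- Every exclusion before V2 also loses V3, so losses at week 12 can never be fewer than losses at week 3.

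**4. Scale.**

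- One patient is 1/16 = 6.25% of an arm.
- The only attrition figure is the 20% dropout rate: 0.20 × 16 = 3.2 per arm, 0.20 × 32 = 6.4 in total. It is not split between withdrawal and exclusion.
- Illustration, assuming that all 20% were early exits at a constant hazard: the proportion lost before V2 is 1 − 0.8^(2/12) = 0.0365 or 1 − 0.8^(2/11) = 0.0398. That is 32 × 0.0365 = 1.2 or 32 × 0.0398 = 1.3 patients lacking week 3, against 6.4 lacking week 12.
- If instead 30% to 70% of the losses came before V2, 0.30 × 6.4 = 1.9 to 0.70 × 6.4 = 4.5 patients would lack week 3. These figures show the ordering only; they do not estimate exclusions.

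**The case against.** **The affected group may be very small.** Only events that seriously endanger the patient trigger exclusion on safety grounds. Ordinary intolerance falls under 4.3.4, which does not end participation. The ethics section expects no risks from a listed flavouring. Severe events soon after platinum and taxane treatment could well stem from the disease or that treatment, and such a patient may be unable to attend in any case. This stands, and it limits the weight of the point. It does not help with non-compliance or protocol violation, where nothing medical prevents a visit.

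**The 20% allowance covers it.** It covers lost numbers, not the reason for the loss.

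**The real defect is the absent missing-data method.** That is a separate gap, and it applies equally to withdrawals under 4.1.2, which rewording 4.1.3 would not recover. But values that could have been measured are better measured than modelled.

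**Blinding protects against bias.** Under Statistical Section 2 the investigators cannot see the randomisation list. A reader might infer that exclusions could be chosen by arm; the documents do not support that. Blinding does not, however, stop a reaction or non-use from depending on the product.

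**The remedy is partial.** After severe events, assessments would still depend on medical judgement, so some product-related loss would remain. This stands.

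**Conclusion.** The point holds: 4.1.3 is a stated rule that discards obtainable outcome data, and a better rule is available at little cost. The main exposure is the 9 week-12 secondary endpoints, 6 of them between arms, with body composition and weight worst placed.

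Three stronger readings are tempting but not supported:

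- **That the primary endpoint is compromised.** It is touched only by exclusion before V2. The first check of medication and diary after V1 is at V2 itself, so non-compliance will usually become demonstrable at or after the primary measurement.
- **That excluded patients leave the intention-to-treat set, or that all nine endpoints are lost outright.** One use of the mouthwash secures membership, four of the outcomes have a V2 value, and the diary keeps partial data.
- **That safety events go unnoticed.** An event that leads to exclusion is already known to the investigator, and stopping for side effects must be reported at once. What is missing is only an explicit rule to follow the event to resolution.

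The conclusion rests on reading exclusion from the study in its ordinary sense, as the end of study visits. The number of patients and the size and direction of any bias cannot be derived from the documents.

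**What to change.** Reword 4.1.3 so that its four reasons lead to permanent discontinuation of the mouthwash rather than exit from the study. When to stop the product remains the sponsor's decision.

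1. **Non-compliance and protocol violation.** The patient attends her remaining V2/V3 visits unless she withdraws consent. Her data enter the intention-to-treat analysis, and the violation affects only the per-protocol set.
2. **Severe adverse events and other medical grounds.** Remaining assessments are done where medically acceptable. The diary is collected when the mouthwash is stopped, and the event is followed in the CRF to resolution or stabilisation.
3. **Suspected HED reaction.** Leave out the test step in section 4.4.1 that involves "administering a 500 ppm caffeine rinse solution with 100 ppm HED added". No endpoint in section 3.3 names this rinse, but the omission is not free: section 4.4.1 also compares caffeine ratings after HED across groups and visits, and that comparison loses the patient's value.
4. **Alignment.** Bring 4.1.2, 4.1.4 (product use as a condition of completion) and 4.3.4 into line.

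Cost: an amendment approved by the investigators and the ethics committee, a CRF field for date and reason of stopping, and staff time for one or two off-product visits that were already planned. Visit payments are 30 + 50 = 80 euros at most per patient. If the whole 20% allowance were exclusions before V2, that would be 6.4 × 80 = 512 euros, and the plan already provides these payments for anyone who attends.

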4.1.4. End of Participation

The patient has completed the study if she has attended all study visits. Study visits must be attended within ± 3 days of the respective appointment. The patient must have taken the prescribed study medication during the specified period. The patient must return the remaining sachets containing the powder at the final examination. All further follow-up visits after the end of the study are conducted, as mentioned above, according to an established follow-up after gynaecologic cancer treatment at the Medical University of Vienna.

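### The single per-protocol set requires attendance to week 12, so for the week-3 primary endpoint membership depends on events after the endpoint was measured

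*Combined protocol and SAP*

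**What the plan says.** Section B, 3. Statistical Analysis gives two analyses of the primary endpoint. ITT takes everyone who used the mouthwash at least once. The other is "Per-protocol analysis: Inclusion of patients who completed the study according to the study protocol". The same two sets serve the secondary endpoints, and no set is tied to a particular endpoint or visit.

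The only definition of completing the study is in Section 4.1.4: "The patient has completed the study if she has attended all study visits". That section adds three conditions: "Study visits must be attended within ± 3 days of the respective appointment"; "The patient must have taken the prescribed study medication during the specified period"; and "The patient must return the remaining sachets containing the powder at the final examination". Section 4.3.4 sets the treatment period: the mouthwash "is administered three times daily before each main meal throughout the entire 12-week study period". Section 4.1.1 puts the last visit, V3, at week 12.

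Sections 3.3 and 4.1.5 confine the primary endpoint to weeks 1 and 3, that is, V1 and V2. Section 4.1.2 states "Withdrawal is defined as premature termination of the study prior to attending Visit 3", so leaving after V2 also counts as withdrawal. It keeps withdrawn patients in the ITT analysis.

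**The concern.** A per-protocol analysis is meant to show the effect in patients who followed the plan up to the measurement. Stopping in week 8 cannot change a score recorded in week 3, yet under the written definitions it removes that score from the per-protocol comparison.

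The reasons for leaving between V2 and V3 may be related to treatment. Section 4.3.4 lets patients stop for side effects, and Section 4.1.3 lets the investigator exclude patients for adverse events or non-compliance. If such reasons differ between arms, the per-protocol week-3 difference is shifted by selection that the endpoint did not require. The set also loses patients with complete primary data. The plan does not say which of the two analyses is the main one or what follows if they disagree, so the per-protocol result could carry weight in the conclusion.

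**Working it through.** **Step 1: the definitions side by side.** Per protocol means completed the study (Section B, 3). Completed means all visits attended (4.1.4). The last visit is V3 at week 12 (4.1.1). The primary endpoint needs only V1 and V2 (3.3, 4.1.5).

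**Step 2: a test case.** A patient attends V1 and V2 in window, uses the mouthwash as prescribed, and leaves in week 8. Both primary measurements exist. She is in the ITT analysis, because she used the mouthwash at least once and withdrawals are kept. She is out of the per-protocol analysis, because V3 is missing.

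**Step 3: the plan's own figure.** Section B, 1 gives 32 patients (16 per arm) with 20% dropout, 90% power and 1% significance, for a 30% reduction with SD 10%. These inputs do not reproduce 32. The two-sided normal approximation gives 2 × 14.88 × (10/30)² = 3.3, so 4 per arm, or 5 after dropout (10 in total). The exact two-sample t-test needs 6 per arm (power 95.6%; 5 per arm gives 87.4%), or 8 after dropout (16 in total). This is a separate matter. The counts below use only the stated 32 and 20%.

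**Step 4: set sizes.** Expected dropouts are 0.20 × 32 = 6.4. Let *s* be the share of them who leave after V2.

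- Written per-protocol set: at most 32 − 6.4 = 25.6 (12.8 per arm), whatever *s* is.
- Set defined to V2: at most 25.6 + 6.4*s*.
- Patients with both measurements left out by the written rule: 6.4*s*.
- Standard error ratio, with equal arms and a common SD: √[(25.6 + 6.4*s*)/25.6] = √(1 + 0.25*s*).

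| *s* | Set to V2 | Left out | Left out as share of set to V2 | SE ratio |
|---|---|---|---|---|
| 0 | 25.6 | 0 | 0% | 1.00 |
| 0.5 | 28.8 | 3.2 | 11% | 1.06 |
| 9/11 (uniform, V3 11 weeks after V1) | 30.8 | 5.2 | 17% | 1.10 |
| 10/12 (uniform, V3 12 weeks after V1) | 30.9 | 5.3 | 17% | 1.10 |
| 1 | 32.0 | 6.4 | 20% | 1.12 |

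The documents give no dropout timing, so *s* is unknown and the uniform rows are an assumption. Both sets are upper limits, since window, compliance and other violations remove further patients. A patient who stops the mouthwash after V2 but attends V3 is not counted here. She would also be out if the medication condition in 4.1.4 is part of completing according to protocol.

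**Step 5: the date of V3.** The visit text says "The patient returns 12 weeks after the end of her last chemotherapy session for a final examination", which is day 84 after chemotherapy. The overview table in the same section puts V3 12 weeks after V1; with V1 at one week, that is day 7 + 84 = 91. At ±3 days the windows are days 81–87 and 88–94, which do not overlap. If the window is judged against the scheduled date, per-protocol membership for a week-3 endpoint could turn on this discrepancy. The two statements must be reconciled.

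**The case against.** The strongest reply is that ITT protects the primary comparison. It is listed first and keeps every patient in question. That stands. A reader might infer that the trial throws away about 17% of its primary data; the documents do not support this, because the loss is confined to the per-protocol analysis and the figure depends on assumed dropout timing.

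A reader might also infer that the rule enriches the HED arm for responders. Nothing in the documents says that women without benefit leave more often. If they did, placebo non-responders could leave too (Section C, 1.1 expects some placebo effect), and women whose taste had recovered might also stop. The direction is unknown.

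Any per-protocol set selects after randomisation, including one defined to V2. That is true: the change removes selection after the outcome but does not restore the randomised comparison.

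The 20% stands in the sample-size paragraph for the week-3 endpoint and may mean loss before week 3. Then *s* is 0 for those dropouts, and later leavers would come on top in a number the plan does not give. The range must therefore start at zero. Nor does the wider standard error threaten the planned power on the plan's own inputs: 12.8 per arm is what remains after the dropout already allowed for, and the stated effect and SD need only 6.

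Finally, Section B, 3 does not cite 4.1.4, which is not written as an analysis-set definition. But it is the only definition of completion, and a reader applying the plan has no other.

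**Conclusion.** The point holds for the per-protocol analysis only. As written, patients with complete and compliant week-3 data leave the per-protocol primary comparison because of events between V2 and V3. This is avoidable selection after the outcome, of unknown direction. At the planned 20% dropout it costs that set 0 to 6.4 patients in total and widens its standard error by 0 to 12%; under uniform dropout, an assumption, the figures are about 5 patients and 10%. The conclusion rests on reading completion in Section B, 3 as defined in 4.1.4. Completion to week 12 suits the week-12 secondary endpoints; the fault is using the same set for week 3. The change should be made, but the defect does not undermine the ITT result.

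**What to change.** Before unblinding, replace the single per-protocol definition in Section B, 3 with sets defined by endpoint:

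- **Week-3 endpoints** (the primary and the week-3 secondary endpoints): V1 and V2 attended in window, mouthwash used as planned up to V2, and no major violation up to V2.
- **Week-12 endpoints:** the same conditions up to V3.

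Leave the ITT set unchanged. State that 4.1.4 describes the end of participation and does not define an analysis set, and reconcile the two statements of the V3 date so that the V3 window can be applied. The cost is a sentence or two in the analysis section and a clarification of the visit schedule; no new patients, visits or data are needed.
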